10.5 Plans for Interim Analysis

No interim analyses were planned or performed for this study.

10.6 Handling of Missing Data

All summaries will be performed only on subjects undergoing the surgical procedure and only observed data will be summarized. There will be no imputation of data for early terminated subjects or for missing data within the database.

10.7 Sensitivity Analyses

Analyses of the primary performance and safety endpoints will be replicated on the Per Protocol Set to assess the primary results in the set of subjects with no major protocol violations.

10.8 Subgroup Analysis

No subgroup analyses are planned for this study.

10.9 Assessment of Site Homogeneity

No summaries or adjustments by study site are planned for this study.

10.10 Additional Endpoint Analyses

Device usage details will be summarized with counts and percentages for subjects in whom the device was articulated during the surgical procedure. Summaries will be provided by randomized treatment group and in total. Similar summaries will also be provided for the surgeon satisfaction questionnaire and the surgeon device questionnaire (administered only in PVS cases).

Post-operative pain is assessed at Visit 3 and Visit 4. Subjects are asked to rate their pain on a scale ranging from 0 (no pain) to 10 (worst possible pain). Subjects will rate pain relating to three sites – trocar site, incisional site, and chest tube site. Summary statistics will be provided at Visits 3 and 4, as well as the change from Visit 3 to Visit 4. No inferential comparisons between treatment groups are planned.

Summary statistics will be provided for the Surgery Task Load Index (Surg-TLX). Surgeons are asked to rate 6 specific components after each surgery performed. The 6 components are – mental fatigue, physical fatigue, hurried/rushed pace, procedure complexity, anxious while performing procedure, and distracting operating environment. Each component is scored on a 0 to 100 scale with lower scores representing a ‘Low’ response on that component and higher scores indicating a ‘High’ response on that component. Summaries will also be provided for an overall score which is calculated as the average of the six components for each surgery.

The ASES Shoulder Assessment is a patient reported outcome designed to measure functional limitations and pain of the shoulder and has been adapted to this study to measure upper body functionality following VATS lobectomy. The assessment utilizes 10 questions that are answered with: unable to do = 0, very difficult to do = 1, somewhat difficult to do = 2, and not difficult = 3. Scores for each subject are obtained by summing the responses to the 10 questions and thus range from 0 to 30. Summary statistics will be provided for the ASES Shoulder Assessment at Visit 1 (prior to surgery), Visit 3 (after surgery, prior to discharge), and Visit 4 (approximately 4 weeks after surgery). Summary statistics will also be provided for the change from Visit 1 to Visit 3, and for the change from Visit 1 to Visit 4.

The total number of protocol deviations will be tabulated by treatment group and in total. Specific types of protocol deviations will also be summarized with counts and percentages. The number and percentage of subjects with at least one protocol deviation will also be summarized.

10.11 Safety Analyses

Safety will be assessed through the incidence of adverse events (AEs) and serious adverse events (SAEs), which will be coded using the Medical Dictionary for Regulatory Activities (MedDRA). The number and percentage of subjects reporting AEs and SAEs will be summarized at the MedDRA system organ class and preferred term level by treatment group and overall. Similar summaries will also be provided for AEs and SAEs related to the study device, as well as for AEs and SAEs related to the study procedure. Related events are those where the relationship is indicated as Possibly, Related, or Unknown. The incidence of AEs will also be summarized by maximum severity. All reported adverse events will be listed.

Appendix: Table Shells and List of Listings to be Generated

Table shells are provided below for all summaries to be generated for this study. Additionally, a list of all listings to be created is provided corresponding to the eCRFs that were used during this study. All fields collected will be listed.

Table 1
Subject Disposition
All Subjects

	Standard of Care Stapler	Powered Vascular Stapler	Total
Signed Informed Consent			xx
Randomized	xx	xx	xx
Safety Set	xx (xx.x%)	xx (xx.x%)	xx (xx.x%)
Full Analysis Set	xx (xx.x%)	xx (xx.x%)	xx (xx.x%)
Completed the Study	xx (xx.x%)	xx (xx.x%)	xx (xx.x%)
Discontinued from the Study	xx (xx.x%)	xx (xx.x%)	xx (xx.x%)
Reason for Discontinuation			
Withdrawal of consent	xx (xx.x%)	xx (xx.x%)	xx (xx.x%)
Surgical	xx (xx.x%)	xx (xx.x%)	xx (xx.x%)
Adverse Event	xx (xx.x%)	xx (xx.x%)	xx (xx.x%)
Death	xx (xx.x%)	xx (xx.x%)	xx (xx.x%)
Lost to Follow-up	xx (xx.x%)	xx (xx.x%)	xx (xx.x%)
Site or Study Termination	xx (xx.x%)	xx (xx.x%)	xx (xx.x%)
Other	xx (xx.x%)	xx (xx.x%)	xx (xx.x%)

Note: All percentages are based on the number of subjects in the Safety Set as the denominator.

Table 2
 Subject Demographics
 Full Analysis Set

Characteristics	Standard of Care Stapler (N = ##)	Powered Vascular Stapler (N = ##)	Overall (N = ##)
Race			
White	xx (xx.x%)	xx (xx.x%)	xx (xx.x%)
Black or African American	xx (xx.x%)	xx (xx.x%)	xx (xx.x%)
American Indian or Alaska Native	xx (xx.x%)	xx (xx.x%)	xx (xx.x%)
Native Hawaiian or Other Pacific Islander	xx (xx.x%)	xx (xx.x%)	xx (xx.x%)
Asian	xx (xx.x%)	xx (xx.x%)	xx (xx.x%)
Other	xx (xx.x%)	xx (xx.x%)	xx (xx.x%)
Ethnicity			
Hispanic	xx (xx.x%)	xx (xx.x%)	xx (xx.x%)
Non-Hispanic	xx (xx.x%)	xx (xx.x%)	xx (xx.x%)
Age (years)			
n	xx	xx	xx
Mean	xx.x	xx.x	xx.x
Standard Deviation	x.xxx	x.xxx	x.xxx
Median	xx.x	xx.x	xx.x
Minimum, Maximum	xx.x, xx.x	xx.x, xx.x	xx.x, xx.x
Gender			
Male	xx (xx.x%)	xx (xx.x%)	xx (xx.x%)
Female	xx (xx.x%)	xx (xx.x%)	xx (xx.x%)

Table 3
Protocol Deviations
Safety Set

Characteristics	Standard of Care Stapler (N = ##)	Powered Vascular Stapler (N = ##)	Overall (N = ##)
Total Number of Protocol Deviations	xxx	xxx	xxx
Specific Types of Protocol Deviations [1]			
Informed Consent Process	xx (xx.x%)	xx (xx.x%)	xx (xx.x%)
Inclusion/Exclusion Criteria	xx (xx.x%)	xx (xx.x%)	xx (xx.x%)
Randomization	xx (xx.x%)	xx (xx.x%)	xx (xx.x%)
Study Procedure	xx (xx.x%)	xx (xx.x%)	xx (xx.x%)
Visit Out of Window	xx (xx.x%)	xx (xx.x%)	xx (xx.x%)
Other	xx (xx.x%)	xx (xx.x%)	xx (xx.x%)
Sponsor Assessment of Protocol Deviations [1]			
Minor	xx (xx.x%)	xx (xx.x%)	xx (xx.x%)
Major	xx (xx.x%)	xx (xx.x%)	xx (xx.x%)
Number (%) of Subjects With at Least 1 Protocol Deviation [2]	xx (xx.x%)	xx (xx.x%)	xx (xx.x%)

1. Denominator used is the total number of protocol deviations reported.
2. Denominator used is the total number of subjects in the column header.

Table 4
 Surgical Characteristics
 Full Analysis Set

Characteristics	Standard of Care Stapler (N = ##)	Powered Vascular Stapler (N = ##)	Overall (N = ##)
Location of Affected Lobe			
Left Lung, Superior Lobe	xx (xx.x%)	xx (xx.x%)	xx (xx.x%)
Left Lung, Inferior Lobe	xx (xx.x%)	xx (xx.x%)	xx (xx.x%)
Left Lung, Multiple Lobes	xx (xx.x%)	xx (xx.x%)	xx (xx.x%)
Right Lung, Superior Lobe	xx (xx.x%)	xx (xx.x%)	xx (xx.x%)
Right Lung, Middle Lobe	xx (xx.x%)	xx (xx.x%)	xx (xx.x%)
Right Lung, Inferior Lobes	xx (xx.x%)	xx (xx.x%)	xx (xx.x%)
Right Lung, Multiple Lobes	xx (xx.x%)	xx (xx.x%)	xx (xx.x%)
Calcified Hilar Lymph Nodes Present?			
Yes	xx (xx.x%)	xx (xx.x%)	xx (xx.x%)
No	xx (xx.x%)	xx (xx.x%)	xx (xx.x%)
Number of Pulmonary Arteries Transected			
0	xx (xx.x%)	xx (xx.x%)	xx (xx.x%)
1	xx (xx.x%)	xx (xx.x%)	xx (xx.x%)
2	xx (xx.x%)	xx (xx.x%)	xx (xx.x%)
3	xx (xx.x%)	xx (xx.x%)	xx (xx.x%)
Number of Ports			
1	xx (xx.x%)	xx (xx.x%)	xx (xx.x%)
2	xx (xx.x%)	xx (xx.x%)	xx (xx.x%)
3	xx (xx.x%)	xx (xx.x%)	xx (xx.x%)
4	xx (xx.x%)	xx (xx.x%)	xx (xx.x%)
Number of Chest Tubes Placed Intraoperatively			
0	xx (xx.x%)	xx (xx.x%)	xx (xx.x%)
1	xx (xx.x%)	xx (xx.x%)	xx (xx.x%)
2	xx (xx.x%)	xx (xx.x%)	xx (xx.x%)
ASA Physical Status			
Class I	xx (xx.x%)	xx (xx.x%)	xx (xx.x%)
Class II	xx (xx.x%)	xx (xx.x%)	xx (xx.x%)
Class III	xx (xx.x%)	xx (xx.x%)	xx (xx.x%)

Table 4
 Surgical Characteristics
 Full Analysis Set

Characteristics	Standard of Care Stapler (N = ##)	Powered Vascular Stapler (N = ##)	Overall (N = ##)
Estimated Blood Loss (mL)			
n	XX	XX	XX
Mean	XX.X	XX.X	XX.X
Standard Deviation	X.XXX	X.XXX	X.XXX
Median	XX.X	XX.X	XX.X
Minimum, Maximum	XX.X, XX.X	XX.X, XX.X	XX.X, XX.X
Transfusion of Blood or Blood Product Required?			
Yes	XX (xx.x%)	XX (xx.x%)	XX (xx.x%)
No	XX (xx.x%)	XX (xx.x%)	XX (xx.x%)
Procedure Converted to Open?			
Yes	XX (xx.x%)	XX (xx.x%)	XX (xx.x%)
No	XX (xx.x%)	XX (xx.x%)	XX (xx.x%)
Procedure Duration (min)			
n	XX	XX	XX
Mean	XX.X	XX.X	XX.X
Standard Deviation	X.XXX	X.XXX	X.XXX
Median	XX.X	XX.X	XX.X
Minimum, Maximum	XX.X, XX.X	XX.X, XX.X	XX.X, XX.X
Chest Tube Duration (nights)			
n	XX	XX	XX
Mean	XX.X	XX.X	XX.X
Standard Deviation	X.XXX	X.XXX	X.XXX
Median	XX.X	XX.X	XX.X
Minimum, Maximum	XX.X, XX.X	XX.X, XX.X	XX.X, XX.X

Programming Note: Chest tube duration is calculated from date of surgery to date of final chest tube removal

Table 5
 Tumor Assessment – Pathology Lab
 Full Analysis Set

Characteristics	Standard of Care Stapler (N = ##)	Powered Vascular Stapler (N = ##)	Overall (N = ##)
Tumor Stage, Confirmed by Pathology			
Stage 0	xx (xx.x%)	xx (xx.x%)	xx (xx.x%)
Stage IA	xx (xx.x%)	xx (xx.x%)	xx (xx.x%)
Stage IB	xx (xx.x%)	xx (xx.x%)	xx (xx.x%)
Stage IIA	xx (xx.x%)	xx (xx.x%)	xx (xx.x%)
Stage IIB	xx (xx.x%)	xx (xx.x%)	xx (xx.x%)
Stage IIIA	xx (xx.x%)	xx (xx.x%)	xx (xx.x%)
Stage IIIB	xx (xx.x%)	xx (xx.x%)	xx (xx.x%)
Stage IV	xx (xx.x%)	xx (xx.x%)	xx (xx.x%)
Maximum Tumor Diameter (cm)			
n	xx	xx	xx
Mean	xx.x	xx.x	xx.x
Standard Deviation	x.XXX	X.XXX	X.XXX
Median	xx.x	xx.x	xx.x
Minimum, Maximum	xx.x, xx.x	xx.x, xx.x	xx.x, xx.x
Maximum Tumor Depth (cm)			
n	xx	xx	xx
Mean	xx.x	xx.x	xx.x
Standard Deviation	x.XXX	X.XXX	X.XXX
Median	xx.x	xx.x	xx.x
Minimum, Maximum	xx.x, xx.x	xx.x, xx.x	xx.x, xx.x
Primary Tumor TNM Classification			
TX	xx (xx.x%)	xx (xx.x%)	xx (xx.x%)
T0	xx (xx.x%)	xx (xx.x%)	xx (xx.x%)
Tix	xx (xx.x%)	xx (xx.x%)	xx (xx.x%)
T1	xx (xx.x%)	xx (xx.x%)	xx (xx.x%)
T1a	xx (xx.x%)	xx (xx.x%)	xx (xx.x%)
T1b	xx (xx.x%)	xx (xx.x%)	xx (xx.x%)
T2	xx (xx.x%)	xx (xx.x%)	xx (xx.x%)
T3	xx (xx.x%)	xx (xx.x%)	xx (xx.x%)
T4	xx (xx.x%)	xx (xx.x%)	xx (xx.x%)

Table 5
Tumor Assessment – Pathology Lab
Full Analysis Set

Characteristics	Standard of Care Stapler (N = ##)	Powered Vascular Stapler (N = ##)	Overall (N = ##)
TNM Classification for Regional Lymph Node			
NX	xx (xx.x%)	xx (xx.x%)	xx (xx.x%)
N0	xx (xx.x%)	xx (xx.x%)	xx (xx.x%)
N1	xx (xx.x%)	xx (xx.x%)	xx (xx.x%)
N2	xx (xx.x%)	xx (xx.x%)	xx (xx.x%)
N3	xx (xx.x%)	xx (xx.x%)	xx (xx.x%)
Distant Metastasis Present?			
Yes	xx (xx.x%)	xx (xx.x%)	xx (xx.x%)
No	xx (xx.x%)	xx (xx.x%)	xx (xx.x%)
Tumor Confirmed by Pathology as Non-Small Cell Lung Cancer?			
Yes	xx (xx.x%)	xx (xx.x%)	xx (xx.x%)
No	xx (xx.x%)	xx (xx.x%)	xx (xx.x%)

Table 6
 Intra-Operative Interventions on Pulmonary Artery or Pulmonary Vein
 Full Analysis Set

Characteristics	Standard of Care Stapler (N = ##)	Powered Vascular Stapler (N = ##)	Overall (N = ##)
Total Number of Vessels Transected	XXX	XXX	XXX
Pulmonary Artery	XXX	XXX	XXX
Pulmonary Vein	XXX	XXX	XXX
Number of Vessel Transections Requiring Intervention [1] n (%)	xx (xx.x%) xx.x%, xx.x%	xx (xx.x%) xx.x%, xx.x%	xx (xx.x%) xx.x%, xx.x%
95% Confidence Interval for Percent			
Difference (95% CI) for Percent Requiring Transection [2]		xx.x% (xx.x%, xx.x%)	
Type of Intervention, n (%) [3]			
Additional Stapling	xx (xx.x%)	xx (xx.x%)	xx (xx.x%)
Over-sewing	xx (xx.x%)	xx (xx.x%)	xx (xx.x%)
Compression	xx (xx.x%)	xx (xx.x%)	xx (xx.x%)
Use of Suture	xx (xx.x%)	xx (xx.x%)	xx (xx.x%)
Sealant	xx (xx.x%)	xx (xx.x%)	xx (xx.x%)
Buttress	xx (xx.x%)	xx (xx.x%)	xx (xx.x%)
Use of Energy	xx (xx.x%)	xx (xx.x%)	xx (xx.x%)
Clip Placement	xx (xx.x%)	xx (xx.x%)	xx (xx.x%)
Blood Product Transfusion	xx (xx.x%)	xx (xx.x%)	xx (xx.x%)
Additional Surgical Procedure	xx (xx.x%)	xx (xx.x%)	xx (xx.x%)
Other Intervention	xx (xx.x%)	xx (xx.x%)	xx (xx.x%)

[1] Denominator for calculation of percentage is the total number of vessels transected in that group.

[2] Difference is calculated as Powered Vascular Stapler minus Standard of Care Stapler.

[3] Denominator for calculation of percentage is the total number of vessels requiring intervention in that group.

Table 7
Post-Operative Interventions or Procedures Related to Pulmonary Artery or Pulmonary Vein Bleeding
Safety Set

Characteristics	Standard of Care Stapler (N = ##)	Powered Vascular Stapler (N = ##)	Overall (N = ##)
Number of Subjects Requiring Post-Operative Intervention Related to Pulmonary Artery or Pulmonary Vein Bleeding			
n (%) [1]	xx (xx.x%)	xx (xx.x%)	xx (xx.x%)
95% Confidence Interval for Percent	xx.x%, xx.x%	xx.x%, xx.x%	xx.x%, xx.x%
Type of Intervention, n (%) [2]			
Blood Product Transfusion	xx (xx.x%)	xx (xx.x%)	xx (xx.x%)
Additional Surgical Procedure	xx (xx.x%)	xx (xx.x%)	xx (xx.x%)
Other Intervention	xx (xx.x%)	xx (xx.x%)	xx (xx.x%)

[1] Denominator for calculation of percentage is the total number of subjects in that group.

[2] Denominator for calculation of percentage is the total number of subjects requiring intervention in that group.

Table 8
Device Usage Details
Full Analysis Set

Characteristics	Standard of Care Stapler (N = ##)	Powered Vascular Stapler (N = ##)	Overall (N = ##)
Number of Subjects Where Device Was Articulated	xxx	xxx	xxx
Did Articulation Make it Easier to Perform Surgery? [1]			
Yes	xx (xx.x%)	xx (xx.x%)	xx (xx.x%)
No	xx (xx.x%)	xx (xx.x%)	xx (xx.x%)
Was Articulation Essential to Performing the Surgery? [1]			
Yes	xx (xx.x%)	xx (xx.x%)	xx (xx.x%)
No	xx (xx.x%)	xx (xx.x%)	xx (xx.x%)
Was the Angle Range of the Device Sufficient? [1]			
Yes	xx (xx.x%)	xx (xx.x%)	xx (xx.x%)
No	xx (xx.x%)	xx (xx.x%)	xx (xx.x%)

1. Denominator used is the total number of subjects in whom the device was articulated.

Table 9
 Surgery Task Load Index (SURG-TLX)
 Full Analysis Set

Characteristic	Standard of Care Stapler (N = ##)	Powered Vascular Stapler (N = ##)	Overall (N = ##)
Overall Score			
n	XX	XX	XX
Mean	XX.X	XX.X	XX.X
Standard Deviation	X.XXX	X.XXX	X.XXX
Median	XX.X	XX.X	XX.X
Minimum, Maximum	XX.X, XX.X	XX.X, XX.X	XX.X, XX.X
Mentally Fatiguing			
n	XX	XX	XX
Mean	XX.X	XX.X	XX.X
Standard Deviation	X.XXX	X.XXX	X.XXX
Median	XX.X	XX.X	XX.X
Minimum, Maximum	XX.X, XX.X	XX.X, XX.X	XX.X, XX.X
Physically Fatiguing			
n	XX	XX	XX
Mean	XX.X	XX.X	XX.X
Standard Deviation	X.XXX	X.XXX	X.XXX
Median	XX.X	XX.X	XX.X
Minimum, Maximum	XX.X, XX.X	XX.X, XX.X	XX.X, XX.X
Similar summaries for remaining components: Hurried/Rushed Pace Procedure Complexity Anxious While Performing Procedure Distracting Operating Environment			

Note: Each component is scored on a 0 to 100 scale with lower scores representing a 'Low' response
 and higher scores representing a 'High' response.

Table 10
Surgeon Satisfaction Questionnaire
Full Analysis Set

Characteristics	Standard of Care Stapler (N = ##)	Powered Vascular Stapler (N = ##)	Overall (N = ##)
How Satisfied Were You With Device Usability?			
Very Unsatisfied	xx (xx.x%)	xx (xx.x%)	xx (xx.x%)
Unsatisfied	xx (xx.x%)	xx (xx.x%)	xx (xx.x%)
Neutral	xx (xx.x%)	xx (xx.x%)	xx (xx.x%)
Satisfied	xx (xx.x%)	xx (xx.x%)	xx (xx.x%)
Very Satisfied	xx (xx.x%)	xx (xx.x%)	xx (xx.x%)
Amount of Tissue Slippage			
No Tissue Slippage	xx (xx.x%)	xx (xx.x%)	xx (xx.x%)
Some Tissue Slippage	xx (xx.x%)	xx (xx.x%)	xx (xx.x%)
Extensive Tissue Slippage	xx (xx.x%)	xx (xx.x%)	xx (xx.x%)

Table 11
 Post-Operative Pain Score
 Full Analysis Set

Pain Component	Time Point Statistic	Standard of Care Stapler (N = ##)	Powered Vascular Stapler (N = ##)	Overall (N = ##)
Trocar Pain	Visit 3			
	n	XX	XX	XX
	Mean	XX.X	XX.X	XX.X
	Standard Deviation	X.XXX	X.XXX	X.XXX
	Median	XX.X	XX.X	XX.X
	Minimum, Maximum	XX.X, XX.X	XX.X, XX.X	XX.X, XX.X
	Visit 4			
	n	XX	XX	XX
	Mean	XX.X	XX.X	XX.X
	Standard Deviation	X.XXX	X.XXX	X.XXX
	Median	XX.X	XX.X	XX.X
	Minimum, Maximum	XX.X, XX.X	XX.X, XX.X	XX.X, XX.X
	Change From Visit 3 to Visit 4			
	n	XX	XX	XX
	Mean	XX.X	XX.X	XX.X
	Standard Deviation	X.XXX	X.XXX	X.XXX
	Median	XX.X	XX.X	XX.X
	Minimum, Maximum	XX.X, XX.X	XX.X, XX.X	XX.X, XX.X

Same summary will be repeated for:

Incisional Pain
 Chest Tube Pain

Programming note: Change from Visit 3 to Visit 4 will be calculated as Visit 4 value minus Visit 3 value.

Note: For each pain component, the subject is asked to rate his or her pain today on a scale from 0 (no pain) to 10 (worst possible pain).

Table 12
Surgeon Device Questionnaire
Full Analysis Set

Question Response	Powered Vascular Stapler (N = ##)

The ECHELON FLEX Powered Vascular Stapler with Advanced Placement Tip enables easier placement of the device on vessels compared to your current standard of care device:
 
Strongly Disagree Slightly Disagree Neutral Agree Strongly Agree
	
xx (xx.x%) xx (xx.x%) xx (xx.x%) xx (xx.x%) xx (xx.x%)

The ECHELON FLEX Powered Vascular Stapler with Advanced Placement Tip has the potential to reduce the amount of dissection required (otomy) around the vessel to place the stapler compared to your current standard of care device:
 
Strongly Disagree Slightly Disagree Neutral Agree Strongly Agree
	
xx (xx.x%) xx (xx.x%) xx (xx.x%) xx (xx.x%) xx (xx.x%)

The ECHELON FLEX Powered Vascular Stapler with Advanced Placement Tip has the potential to reduce the surgeon stress during the most challenging step of the procedure, which is the pulmonary artery / pulmonary vein transection, compared to your current standard of care device:
 
Strongly Disagree Slightly Disagree Neutral Agree Strongly Agree
	
xx (xx.x%) xx (xx.x%) xx (xx.x%) xx (xx.x%) xx (xx.x%)

The ECHELON FLEX Powered Vascular Stapler with Advanced Placement Tip allows for the precise control and placement of the end effector on the target vessel compared to your current standard of care device:
 
Strongly Disagree Slightly Disagree Neutral Agree Strongly Agree
	
xx (xx.x%) xx (xx.x%) xx (xx.x%) xx (xx.x%) xx (xx.x%)

Table 13
 ASES Shoulder Assessment
 Full Analysis Set

Shoulder Side	Time Point Statistic	Standard of Care Stapler (N = ##)	Powered Vascular Stapler (N = ##)	Overall (N = ##)
Right	Visit 1			
	n	XX	XX	XX
	Mean	XX.X	XX.X	XX.X
	Standard Deviation	X.XXX	X.XXX	X.XXX
	Median	XX.X	XX.X	XX.X
	Minimum, Maximum	XX.X, XX.X	XX.X, XX.X	XX.X, XX.X
	Visit 3			
	n	XX	XX	XX
	Mean	XX.X	XX.X	XX.X
	Standard Deviation	X.XXX	X.XXX	X.XXX
	Median	XX.X	XX.X	XX.X
	Minimum, Maximum	XX.X, XX.X	XX.X, XX.X	XX.X, XX.X
	Change From Visit 1 to Visit 3			
	n	XX	XX	XX
	Mean	XX.X	XX.X	XX.X
	Standard Deviation	X.XXX	X.XXX	X.XXX
	Median	XX.X	XX.X	XX.X
	Minimum, Maximum	XX.X, XX.X	XX.X, XX.X	XX.X, XX.X
	Visit 4			
	n	XX	XX	XX
	Mean	XX.X	XX.X	XX.X
	Standard Deviation	X.XXX	X.XXX	X.XXX
	Median	XX.X	XX.X	XX.X
	Minimum, Maximum	XX.X, XX.X	XX.X, XX.X	XX.X, XX.X
	Change From Visit 1 to Visit 4			
	n	XX	XX	XX
	Mean	XX.X	XX.X	XX.X
	Standard Deviation	X.XXX	X.XXX	X.XXX
	Median	XX.X	XX.X	XX.X
	Minimum, Maximum	XX.X, XX.X	XX.X, XX.X	XX.X, XX.X

Same summary will be repeated for: Left Side

Programming note: Change from Visit 1 to Visit 3 will be calculated as Visit 3 value minus Visit 1 value.

Table 14
 Adverse Events by System Organ Class and Preferred Term
 Safety Set

System Organ Class	Preferred Term	Standard of Care Stapler (N = ##)	Powered Vascular Stapler (N = ##)	Overall (N = ##)
Total		xx (xx.x%)	xx (xx.x%)	xx (xx.x%)
System Organ Class 1	Preferred Term 1	xx (xx.x%)	xx (xx.x%)	xx (xx.x%)
	Preferred Term 2	xx (xx.x%)	xx (xx.x%)	xx (xx.x%)
	Preferred Term 3	xx (xx.x%)	xx (xx.x%)	xx (xx.x%)
System Organ Class 2	Preferred Term 1	xx (xx.x%)	xx (xx.x%)	xx (xx.x%)
	Preferred Term 2	xx (xx.x%)	xx (xx.x%)	xx (xx.x%)
System Organ Class 3	Preferred Term 1	xx (xx.x%)	xx (xx.x%)	xx (xx.x%)
	Preferred Term 2	xx (xx.x%)	xx (xx.x%)	xx (xx.x%)
	Preferred Term 3	xx (xx.x%)	xx (xx.x%)	xx (xx.x%)
System Organ Class 4	Preferred Term 1	xx (xx.x%)	xx (xx.x%)	xx (xx.x%)
	Preferred Term 2	xx (xx.x%)	xx (xx.x%)	xx (xx.x%)

The following tables will have the same format as Table 14:

Table 15	Serious Adverse Events by System Organ Class and Preferred Term Safety Set
Table 16	Adverse Events Related to the Study Device by System Organ Class and Preferred Term Safety Set
Table 17	Serious Adverse Events Related to the Study Device by System Organ Class and Preferred Term Safety Set
Table 18	Adverse Events Related to the Study Procedure by System Organ Class and Preferred Term Safety Set
Table 19	Serious Adverse Events Related to the Study Procedure by System Organ Class and Preferred Term Safety Set

Table 20
 Adverse Events by System Organ Class, Preferred Term and Maximum Severity
 Safety Set

System Organ Class	Preferred Term	Standard of Care Stapler (N = ##)	Powered Vascular Stapler (N = ##)	Overall (N = ##)
Total		xx (xx.x%)	xx (xx.x%)	xx (xx.x%)
Mild		xx (xx.x%)	xx (xx.x%)	xx (xx.x%)
Moderate		xx (xx.x%)	xx (xx.x%)	xx (xx.x%)
Severe		xx (xx.x%)	xx (xx.x%)	xx (xx.x%)
System Organ Class 1		xx (xx.x%)	xx (xx.x%)	xx (xx.x%)
Mild		xx (xx.x%)	xx (xx.x%)	xx (xx.x%)
Moderate		xx (xx.x%)	xx (xx.x%)	xx (xx.x%)
Severe		xx (xx.x%)	xx (xx.x%)	xx (xx.x%)
Preferred Term 1		xx (xx.x%)	xx (xx.x%)	xx (xx.x%)
Mild		xx (xx.x%)	xx (xx.x%)	xx (xx.x%)
Moderate		xx (xx.x%)	xx (xx.x%)	xx (xx.x%)
Severe		xx (xx.x%)	xx (xx.x%)	xx (xx.x%)
Preferred Term 2		xx (xx.x%)	xx (xx.x%)	xx (xx.x%)
Mild		xx (xx.x%)	xx (xx.x%)	xx (xx.x%)
Moderate		xx (xx.x%)	xx (xx.x%)	xx (xx.x%)
Severe		xx (xx.x%)	xx (xx.x%)	xx (xx.x%)
System Organ Class 2		xx (xx.x%)	xx (xx.x%)	xx (xx.x%)
Mild		xx (xx.x%)	xx (xx.x%)	xx (xx.x%)
Moderate		xx (xx.x%)	xx (xx.x%)	xx (xx.x%)
Severe		xx (xx.x%)	xx (xx.x%)	xx (xx.x%)
Preferred Term 1		xx (xx.x%)	xx (xx.x%)	xx (xx.x%)
Mild		xx (xx.x%)	xx (xx.x%)	xx (xx.x%)
Moderate		xx (xx.x%)	xx (xx.x%)	xx (xx.x%)
Severe		xx (xx.x%)	xx (xx.x%)	xx (xx.x%)

The following listings will be generated for this study:

Listing 1	Inclusion/Exclusion Criteria All Subjects
Listing 2	Demographics All Subjects
Listing 3	Medical History All Subjects
Listing 4	Surgical History All Subjects
Listing 5	Inclusion/Exclusion at Surgery and ASA Status All Subjects
Listing 6	Procedure Details All Subjects
Listing 7	Procedure Time Duration All Subjects
Listing 8	Intra-Operative Interventions on Pulmonary Artery and Pulmonary Vein All Subjects
Listing 9	Bronchus and Parenchyma Transections All Subjects
Listing 10	Intra-Operative Interventions Not on Pulmonary Artery and Pulmonary Vein All Subjects
Listing 11	Device Usage Details All Subjects
Listing 12	Tumor Assessment Log All Subjects
Listing 13	Surgeon Device Questionnaire (PVS Only) All Subjects
Listing 14	Surgery Task Load Index All Subjects
Listing 15	Surgeon Satisfaction Questionnaire All Subjects

Listing 16	Post-Operative Interventions on Pulmonary Artery and Pulmonary Vein All Subjects
Listing 17	Pain Score Assessment All Subjects
Listing 18	Chest Tube Details Log All Subjects
Listing 19	Adverse Events All Subjects
Listing 20	Concomitant Medications All Subjects
Listing 21	Concomitant Procedures/Interventions All Subjects
Listing 22	Protocol Deviations All Subjects
Listing 23	Completion/Withdrawal All Subjects
Listing 24	Study Visits All Subjects

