7.4 ANALYSIS OF EFFECTIVENESS

Summary statistics and 95% confidence intervals will be provided for the number and frequency of interventions for the set of SOC subjects and PVS subjects separately. This will be performed based on the total number of firings. An intervention is defined as any firing which is classified as hemostasis intervention. To establish that the intervention rate is not increased compared to SOC, a 95% confidence interval for the difference in proportion of firings requiring interventions for PVS minus SOC will be calculated and powered vascular stapler will be considered to have acceptable performance if the upper bound of the 95% confidence interval does not exceed 3%.

Additional endpoints will be summarized with descriptive statistics and 95% confidence intervals as appropriate for continuous or categorical measurements.

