5.1 Primary Performance Endpoint

The primary performance (effectiveness) endpoint in this study was defined as the occurrence of hemostatic interventions/procedures completed for intra-operative bleeding related to the transection of the PA and PV during VATS lobectomy with the use of either the SOC or PVS stapler. Hemostasis interventions or procedures were defined as bleeding detected and controlled intra-operatively (additional stapling, over-sewing, clip placement, compression, use of suture, sealant, and/or buttress, and/or use of energy); or bleeding that occurred intra-operatively requiring blood or blood product transfusion or an additional surgical procedure (e.g. conversion to open). No hemostasis intervention was defined as no bleeding at the staple line or bleeding that stopped after initial blotting of the staple line.

The primary performance endpoint will be summarized at the firing level as multiple firings per subject were expected and observed; that is, the denominator for the primary endpoint will be the total number of firings and the numerator will be the number of firings where an intervention was required.

During development of the protocol with the Notified Body (TUV) following their decision to grant CE mark to the device, a formal hypothesis was not defined for the study; however, to establish that the intervention rate of PVS is not increased compared to SOC, an acceptance criterion was developed and a 95% confidence interval for the difference in proportion of firings requiring interventions for PVS minus SOC will be calculated. The powered vascular stapler will be considered to have acceptable performance if the upper bound of the 95% confidence interval does not exceed 3%.

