10.4 Primary Endpoint Analyses

For the primary performance endpoint, summary statistics and 95% confidence intervals will be provided for the number and frequency of interventions for the set of SOC subjects and PVS subjects separately. This will be performed based on the total number of firings. An intervention is defined as any firing which is classified as a hemostasis intervention. To establish that the intervention rate is not increased compared to SOC, a 95% confidence interval for the difference in the proportion of firings requiring interventions for PVS minus SOC will be calculated and the powered vascular stapler will be considered to have acceptable performance if the upper bound of the 95% confidence interval does not exceed 3%.

The following SAS code will be used to generate 95% confidence intervals for the individual treatment groups as well as the difference between groups:

```
proc sort data=hemo_interv;
  by TrtGroup descending event;
run;
proc freq data=hemo_interv order=data;
  tables TrtGroup*event/binomial riskdiff;
run;
```

This code assumes that the dataset hemo_interv contains one record per firing, the variable ‘TrtGroup’ contains the identifier for randomized treatment group (the SOC group should be listed in the first row of the table), and the variable ‘event’ identifies an occurrence of the primary endpoint with a 1 and no occurrence of the primary endpoint with a 0. The resulting output in the Column 1 Risk Estimates table in the SAS Output Window provides the individual confidence intervals for each treatment group as well as the confidence interval for the difference between groups.

Additional summaries will be provided to tabulate the total number of vessels transected as well as the specific type of vessel that was transected – pulmonary artery or pulmonary vein. The specific types of interventions that were performed will also be tabulated by randomized treatment group.

The same analysis will be replicated for the primary safety endpoint for the occurrence of hemostatic interventions/procedures completed for post-operative bleeding related to the transection of the PA and PV during VATS lobectomy at the subject level. A similar dataset will be created that contains one record per subject and an indicator for whether or not the subject experienced a post-operative intervention event.

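### The primary rate and the 3% rule are defined per firing, but Table 6, the only SAP shell for this result, computes them per vessel transected

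*SAP*

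**What the plan says.** The text and code agree on the unit. Protocol 7.4 bases the acceptance rule on a 95% confidence interval: the "difference in proportion of firings requiring interventions for PVS minus SOC will be calculated", and the upper bound must not exceed 3%. SAP 5.1 says "the denominator for the primary endpoint will be the total number of firings", with the firings that needed an intervention as numerator. SAP 10.4 repeats the rule, and of its SAS program it says "This code assumes that the dataset hemo_interv contains one record per firing". Vessels have a secondary place there: "Additional summaries will be provided to tabulate the total number of vessels transected".

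The SAP appendix states "Table shells are provided below for all summaries to be generated for this study". Table 6 is the only one with the group rates for intra-operative interventions and the difference between arms. Its count row is "Total Number of Vessels Transected" and its rate row is "Number of Vessel Transections Requiring Intervention". Footnote 1 reads "Denominator for calculation of percentage is the total number of vessels transected in that group". Footnote 3 uses vessels requiring intervention as the denominator for the types of intervention. The interval and difference rows name no denominator of their own and refer back to that percentage. The difference row is also mislabelled: it speaks of the percent requiring transection, where intervention is meant. Firings appear in no row or footnote of Tables 1 to 20.

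**The concern.** Table 6 is where the figure compared with 3% will be reported, and this is the trial's only acceptance criterion. The code produces a per-firing interval, while the footnote asks for a per-vessel percentage. A programmer can satisfy both only if every firing transects a separate vessel. If firings outnumber vessels, the table as drawn shows a higher rate and a different upper limit from those the plan specified. In an open-label study, the denominator of the decision figure should not be left to be chosen at programming, when the data may already be visible.

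**Working it through.** **1. The unit behind the plan's own precision figure.** Protocol 7.2 and SAP 8 assume a 6% rate and at least 260 firings per group. The Wald half-width is 1.96 × √(0.06 × 0.94 / 260) = 2.89%, which reproduces the stated 2.9%. The planning figure is therefore per firing.

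**2. Whether the units must coincide.** SAP 2 says the device cuts and staples in one action, so one firing per transection is plausible. No passage says so, however. SAP 10.4 treats vessels as a separate summary, and SAP 5.1 lists additional stapling among the interventions.

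**3. Effect on the upper limit.** The SAP 10.4 code gives Wald limits by default. With x events in n units, p1 = PVS and p0 = SOC:

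upper limit = p1 − p0 + 1.96 × √[p1(1 − p1)/n1 + p0(1 − p0)/n0]

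The documents give no firings-per-vessel ratio, so two assumptions are shown, both with 260 vessels per arm:
- Case A: each intervention adds one firing.
- Case B: the same ratio of firings to vessels applies in both arms.

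| Events PVS / SOC | Denominators PVS / SOC | Upper limit | Meets 3%? |
|---|---|---|---|
| 13 / 15 | 260 / 260 vessels | 3.11% | no |
| 13 / 15 | 273 / 275 firings (A) | 2.99% | yes |
| 14 / 16 | 260 / 260 vessels | 3.24% | no |
| 14 / 16 | 274 / 276 firings (A) | 3.11% | no |
| 14 / 16 | 282 / 282 firings (B, ratio 1.085) | 2.99% | yes |
| 14 / 16 | 300 / 300 firings (B, ratio 1.15) | 2.82% | yes |
| 16 / 16 | 260 / 260 vessels | 4.13% | no |
| 16 / 16 | 276 / 276 firings (A) | 3.90% | no |
| 16 / 16 | 362 / 362 firings (B, ratio 1.39) | 2.99% | yes |

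The 13 / 15 pair in full:
- Per vessel: 5.00% − 5.77% = −0.77%, half-width 3.88%, upper limit 3.11%.
- Per firing: 4.76% − 5.45% = −0.69%, half-width 3.69%, upper limit 2.99%.

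**4. How often the decision differs.** This is an exact binomial enumeration with 260 independent vessels per arm and a true rate of 6% per vessel in both arms. The two units give different decisions in 2.0% of trials in case A and in 7.7% at 300 firings per arm. If 260 firings per arm are held fixed instead and there are fewer vessels, the figures are 2.2% (260 minus events) and 6.2% (226 vessels).

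**The case against.** The strongest reply is that the planned analysis is not in doubt. The protocol, the SAP text and the code all say firings, and SAP 10.4 takes the intervals from that code's output, so Table 6 only displays them. The authors may have written vessels transected as loose wording for firings, in which case the effect is zero.

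The numerical cases can also be challenged:
- Case A is an upper-end assumption. Table 6 lists ten other types of intervention, and no passage says that a re-stapling firing enters the denominator. If half of the interventions add a firing, different decisions fall from 2.0% to about 1.1% of trials; if a quarter do, to about 0.01%.
- The 1.15 ratio behind the 7.7% is assumed and is not an estimate.
- In both 260-vessel scenarios of step 4, essentially every discordant trial is accepted per firing and not per vessel. The shell as drawn is then the stricter version and would not produce a false acceptance.

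Finally, SAP 10.1 counts re-worded footnotes as minor, and aligning Table 6 with SAP 10.4 restores the planned method.

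Most of this stands as a limit on size and on cost. It does not remove the contradiction: footnote 1 still names a different denominator for the decision figure, and nothing in the documents equates the two units. SAP 10.1 may well allow the correction without an amendment. Reporting the decision per vessel would change the planned analysis, and that does need one.

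**Conclusion.** The concern holds. The decision unit is the firing in Protocol 7.4, SAP 5.1 and SAP 10.4, and Table 6 uses vessels transected instead. The contradiction is certain from the text and rests on no calculation.

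Its effect on the result is conditional. It is zero at one firing per vessel, and it changes the decision only for results near 3%. Under the stated assumptions (6% in both arms, independent vessels, 260 vessels per arm), the two units disagree in 2.0% of trials if each intervention adds one firing, and in 7.7% at an assumed ratio of 1.15. Unequal ratios in the two arms are not covered by these two percentages. The point should be fixed before analysis.

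**What to change.** Before analysis:
- Put Table 6's numerator, denominator, group intervals, difference, and footnotes 1 and 3 on firings, as SAP 5.1 and 10.4 specify.
- Add a row for total firings by arm.
- Correct the label of the difference row so that it refers to intervention.
- Keep vessels transected, by artery and vein, as the additional summary.

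If data collection makes one firing equal one vessel transection, state that in the SAP instead.

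The cost is small: one shell is edited and no planned method changes. There is one dependency to check. Protocol 4.7.3.1.2 lists the number of pulmonary arteries, and cartridge counts for bronchus and parenchyma, but no count of firings on the pulmonary artery or vein. SAP 5.1 says multiple firings per subject were observed, so the counts should exist, but this needs to be confirmed.
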